7.2 Study Procedures by Time Point

7.2.1 Visit 1 (Screening – up to 7 Days)

The Screening Visit is to occur within 7 calendar days prior to the start of study drug administration. After the patient has signed the ICF, the following assessments will be performed and recorded in the patient's source documentation/medical record and in the eCRF:

- Administration of informed consent
- Subjects will also be asked to provide additional consent for their participation in a secure, proprietary research subject database administered by Verified Clinical Trials ([VCT], Garden City, NY). The database will utilize partially identified subject information to review subjects' research study history within the database. Participants who are identified as verification failures by VCT, should not be enrolled without documented approval from LB Pharmaceuticals

 At the last subject contact, VCT staff will automatically close out the subject (safety follow-up, ET, or complete) based on the Interactive Response System (IXRS)
- Admission to inpatient unit
- DSM-5 diagnosis of schizophrenia
- MINI 7.0.2
- MINI-Plus BPD 7.0.2
- Review of inclusion and exclusion criteria
- Recording of medical history
- Recording of prior and current medications (e.g., prescription and nonprescription medications)
- Washout of prohibited psychotropic medications (after signing of ICF)
- PANSS, PCRS must be administered before PANSS
- CGI-S
- C-SSRS
- Collection of demographic information
- Physical examination including height
- Body weight, BMI (derived programmatically from body weight and height measurements), and waist circumference
- Vital signs
- Resting 12-lead ECG (triplicate, further information in Section 8.2.3)

Confidential Page 58 of 102

- Collection of blood and urine samples for clinical laboratory tests. Lab results that are exclusionary are presented in Table 14.2 and other information is presented in the footnotes to the SoA (Table)
- Urine pregnancy test for all females of childbearing potential
- Assessment and recording of AEs
- Urine drug screen/blood alcohol test
- AIMS
- BARS
- SAS
- Submission of applicable data to the Endpoint Adjudication Committee for confirmation of eligibility
- Cogstate test practice assessment

7.2.2 Visit 2 (Baseline, Study Day 1)

At this visit, the following assessments will be performed and recorded in the patient's source documentation/medical record and in the eCRF:

- Review of inclusion and exclusion criteria
- Recording of concomitant medications (e.g., prescription and nonprescription medications)
- Targeted physical examination (if applicable)
- Body weight, BMI (derived programmatically from body weight and height measurements), and waist circumference
- Vital signs
- Resting 12-lead ECG (triplicate, further information in Section 8.2.3)
- Collection of blood and urine samples for clinical laboratory tests. Additional information is presented in the footnotes to the SoA (Table)
- Urine pregnancy test for all females of childbearing potential
- Assessment and recording of AEs
- PANSS- patients with improvement of ≥20% in total PANSS score between the Screening and Baseline assessments will be excluded from study participation. PCRS must be administered before PANSS
- CGI-S
- C-SSRS
- Randomization
- Pre-dose PK blood sample will be collected
- Study drug administration

Confidential Page 59 of 102

- PK sample collection for the first 60 patients randomized regardless of cohort at the following timepoints after the morning dose: 15 minutes, 30 minutes, 1, 2, 3, 4, 8, and 24 hours
- AIMS, 3 to 6 hours post-dose
- BARS, 3 to 6 hours post-dose
- SAS, 3 to 6 hours post-dose
- Cogstate test

7.2.3 Study Days 2 Through 7

On Days 2, 3, 4, 5, 6, and 7 each patient may receive the QD administration of study treatment. No other assessments are scheduled; however, AEs observed or reported, and concomitant medications may be recorded. If any assessments are required in order to evaluate an AE, an unscheduled visit may be conducted, at the discretion of the PI.

7.2.4 Visit 3 (Study Day 8)

The following Study Day 8 assessments can be performed on Day 8 ± 1 day; however, they should all be performed on the same day:

- Recording of concomitant medications (e.g., prescription and nonprescription medications)
- Targeted physical examination (if applicable)
- Body weight, BMI (derived programmatically from body weight and height measurements), and waist circumference
- Vital signs
- Resting 12-lead ECG (triplicate, further information in Section 8.2.3)
- Collection of blood and urine samples for clinical laboratory tests. Additional information is presented in the footnotes to the SoA (Table)
- Study drug administration
- PK sample collection patients randomized regardless of cohort at the following timepoints after the morning dose: 15 minutes, 30 minutes, 1, 2, 3, 4, 8, and 24 hours
- Assessment and recording of AEs
- PANSS, PCRS must be administered before PANSS
- CGI-S
- C-SSRS
- AIMS, 3 to 6 hours post-dose
- BARS, 3 to 6 hours post-dose

Confidential Page 60 of 102

• SAS, 3 to 6 hours post-dose

7.2.5 Study Days 9 Through 14

On Days 9, 10, 11, 12, 13, and 14 each patient may receive the QD administration of study treatment. No other assessments are scheduled. However, any AEs observed or reported, and concomitant medications may be recorded. If any assessments are required in order to evaluate an AE, an unscheduled visit may be conducted, at the discretion of the PI.

7.2.6 Visit 4 (Study Day 15)

The following Study Day 15 assessments can be performed on Day 15 \pm 1 day; however, they should all be performed on the same day:

- Recording of concomitant medications (e.g., prescription and nonprescription medications)
- Targeted physical examination (if applicable)
- Bodyweight, BMI (derived programmatically from body weight and height measurements), and waist circumference
- Vital signs
- Resting 12-lead ECG (triplicate, further information in Section 8.2.3)
- Collection of blood and urine samples for clinical laboratory tests. Additional information is presented in the footnotes to the SoA (Table)
- Study drug administration
- Assessment and recording of AEs
- PANSS, PCRS must be administered before PANSS
- CGI-S
- C-SSRS
- AIMS, 3 to 6 hours post-dose
- BARS, 3 to 6 hours post-dose
- SAS, 3 to 6 hours post-dose

7.2.7 Study Days 16 Through 20

On Days 16, 17, 18, 19, 20, each patient may receive QD administration of study treatment. No other assessments are scheduled. However, any AEs observed or reported, and concomitant medications may be recorded. If any assessments are required in order to evaluate an AE, an unscheduled visit may be conducted, at the discretion of the PI.

Confidential Page 61 of 102

7.2.8 Visit 5 (Study Day 21)

The following Study Day 21 assessments can be performed on Day 21 ± 1 day; however, they should all be performed on the same day:

- Recording of concomitant medications (e.g., prescription and nonprescription medications)
- Targeted physical examination (if applicable)
- Bodyweight, BMI (derived programmatically from body weight and height measurements), and waist circumference
- Vital signs
- Resting 12-lead ECG (triplicate, further information in Section 8.2.3)
- Collection of blood and urine samples for clinical laboratory tests. Additional information is presented in the footnotes to the SoA (Table)
- Study drug administration
- PK sample collection first 60 patients randomized regardless of cohort at the following timepoints after the morning dose: 15 minutes, 30 minutes, 1, 2, 3, 4, 8, and 24 hours
- Assessment and recording of AEs
- PANSS, PCRS must be administered before PANSS
- CGI-S
- C-SSRS
- AIMS, 3 to 6 hours post-dose
- BARS, 3 to 6 hours post-dose
- SAS, 3 to 6 hours post-dose

7.2.9 Study Days 22 Through 27

On Days 22, 23, 24, 25, 26, and 27 each patient may receive the QD administration of study treatment. No other assessments are scheduled. However, any AEs observed or reported, and all concomitant medications may be recorded. If any assessments are required in order to evaluate an AE, an unscheduled visit may be conducted, at the discretion of the PI.

7.2.10 Visit 6 (Study Day 28)

On Study Day 28, all assessments should be performed on the same day; the last day of study drug dosing is Day 28 and, if possible, when any patient discontinues prior to this visit, the following assessments will be performed:

• Recording of concomitant medications (e.g., prescription and nonprescription medications)

Confidential Page 62 of 102

- Full physical examination (if applicable)
- Bodyweight, BMI (derived programmatically from body weight and height measurements), and waist circumference
- Vital signs
- Resting 12-lead ECG (triplicate, further information in Section 8.2.3)
- Collection of blood and urine samples for clinical laboratory tests. Additional information is presented in the footnotes to the SoA (Table)
- Study drug administration
- Urine pregnancy test for all females of childbearing potential
- Assessment and recording of AEs
- PANSS. PCRS must be administered before PANSS
- CGI-S
- C-SSRS
- AIMS, 3 to 6 hours post-dose
- BARS, 3 to 6 hours post-dose
- SAS, 3 to 6 hours post-dose
- Cogstate test

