4.1.1.2 QT Prolongation Stopping Criteria

Dosing of an individual patient will cease if any of the following criteria are met:

• An increase in QTcF to >500 msec for male and female patients.

OR

• An increase in QTcF of >60 msec over Baseline.

A confirmation of an abnormal finding meeting the stopping criteria will be required within 15 minutes of the initial QTcF reading.

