Vital Signs ^t	X	X		X		X		X		X		
Adverse Events ^u	X	X	X	X	X	X	X	X	X	X	X	X
Other												
Study Drug Dosing		X	X	X	X	X	X	X	X	X		
PK Sample Collection ^v		X		X				X				
Restart Standard Antipsychotic ^w											X	

a. Screening begins when the ICF is signed and will take place between Day -7 and Day -1; up to a 7-day extension of the screening phase is allowed, if necessary with the approval of the Medical Monitor; screening procedures should be initiated with a sufficient amount of time allotted in order to obtain central laboratory results and ECG results from the central reader prior to randomization. Review of inclusion/exclusion criteria at Baseline will be based on assessments performed during Screening. Hospitalization will begin with the signing of the ICF for patients who are not already hospitalized at the initial Screening Visit.

Confidential Page 55 of 102

Each patient may receive the QD administration of study treatment. No other assessments are scheduled; however, AEs observed or reported, and concomitant medications may be recorded. In case of an AE, an unscheduled visit may be conducted at the discretion of the PI.

c. Stabilization Period is up to 5 days.

d. The Screening assessments to be audio recorded include the MINI 7.0.2, PCRS and SCI-PANSS and are submitted to an independent central reviewer for review and eligibility confirmation.

^{e.} Includes full psychiatric history, DSM-5 diagnosis of schizophrenia, and MINI 7.0.2.

Washout of prohibited medications begins after signing the ICF and after diagnosis of Schizophrenia is confirmed by MINI. Details of medications requiring washout and guidance for washout time required are provided in Appendix 14.4. Prohibited and restricted medications are listed in Table 6.3:

g. Urine drug screen (full panel including opioids) and a blood alcohol test are required at the designated times, but either or both can be conducted at any time during the trial at the discretion of the Investigator.

h. At Screening, Baseline, and final endpoint, SCI-PANSS and CGI-S will be evaluated by a local site rater with central supervision via independent, central review.

SCI-PANSS will be audio recorded at any visit where they are administered. SCI-PANSS assessment should be preceded by the PCRS. Patients with improvement of ≥20%

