in total PANSS score between the Screening and Baseline assessments will be excluded from study participation. SCI-PANSS will be administered first on visits before any other scales, when SCI-PANSS and CGI-S are being administered with the exception of Screening where MINI-Plus BPD 7.0.2 will be administered first.

The Placebo-Control Reminder Script[©] Hassman and Cohen, 2019, Version 5.0 educates clinical trial subjects of key causes of the placebo and nocebo effects, level setting of the subject's study expectations, reminding subjects what a placebo is and how that relates to their reporting of symptoms and potential side effects, and explaining how interactions with research site staff differ from their experience with clinical providers. The PCRS informs subjects that they are to be honest about their symptoms and that the site staff have no expectations of symptom improvement or worsening and will not be disappointed by the subject's responses, and asks subjects to explain in their own words PCRS content to ensure comprehension. The PANSS Rater will read the PCRS before administering the PANSS at each study visit.

- During Screening, patients will undergo a practice assessment of the Cogstate test. On Day 1 and Day 28, the actual Cogstate testing will be performed. Note: Cogstate Battery test creot be done within 8 hours of receiving a benzodiazepine or sleep medication.
- To include height at the Screening Visit only. A full physical examination will be conducted at the Screening Visit and at EoT Visit. At each other study visit, patients will be assessed for continued dosing and any possible physical symptoms and a targeted physical examination may be performed, if indicated.
- k. On Days 1, 8, 15, 21, and 28, the SAS, BARS, and AIMS assessments are to be conducted 3 to 6 hours after the administration of study treatment with the exception of ET Visit.
- 1. If the administration of C-SSRS at Screening highlights the risk of suicide not previously known, in the opinion of the Investigator, the patient should be excluded from the trial. At this visit the "Baseline/Screening" version of the C-SSRS scale will be used.
- m. At all other study visits the "Since Last Visit" version of the C-SSRS scale should be used.
- ^{n.} BMI; derived programmatically from body weight and height measurements.

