7.2.14 Study Procedures for Early Termination and Withdrawal

If a patient is discontinued at any time after randomization into the study, the Investigator will make every effort to follow the patient and complete the follow-up procedures at an ET Visit as follows:

- Recording of concomitant medications (e.g., prescription and nonprescription medications)
- Full physical examination
- Bodyweight, BMI (derived programmatically from body weight and height measurements), and waist circumference
- Vital signs
- Resting 12-lead ECG (triplicate, further information in Section 8.2.3)
- Collection of blood and urine samples for clinical laboratory tests. Additional information is presented in the footnotes to the SoA (Table 7.1)
- Urine pregnancy test for all females of childbearing potential
- Assessment and recording of AEs
- PANSS
- CGI-S
- C-SSRS
- AIMS
- BARS

Confidential Page 64 of 102

- SAS
- Cogstate test

Confidential Page 65 of 102

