9.2.3 Pregnancy During the Study

If a patient, or the female partner of a male patient, becomes pregnant during the study, the Investigator will notify the Sponsor or designated representative immediately after the pregnancy is confirmed. The Investigator will report any pregnancies using the eCRF Pregnancy Reporting Form within 24 hours of becoming aware of the event. The Investigator will also (1) notify the patient's physician that the patient was being treated with LB-102, and (2) follow the progress of the pregnancy and document the outcome of the pregnancy. Pregnancy outcome information should be forwarded to Sponsor or designated representative when available.

Patients who become pregnant during the study will not be eligible for any further study treatments, the study drug will be discontinued immediately, and the patient will complete an ET Visit. The Investigator should make every effort to follow the patient until completion of the pregnancy and complete the Exposure in Utero (EIU) Reporting Form eCRF with complete pregnancy outcome information, including normal delivery and induced abortion. Any adverse pregnancy outcome, either serious or nonserious, should be reported in accordance with study procedures. If the outcome of the pregnancy meets the criteria for immediate classification as an SAE (i.e., post-partum complications, spontaneous or induced abortion, stillbirth, neonatal death, or congenital anomaly, including that of an aborted fetus), the Investigator should follow the procedures for reporting SAEs outlined in Section 9.2.2. In the event the eCRF system is unavailable, a back-up paper Pregnancy Reporting Form will be available for site staff to complete following the reporting guidelines as outlined in Section 9.2.2.

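### Section 7.2.10 and the dosing row of the schedule list study drug for patients who discontinue early, against the stopping rules and the early-termination lists

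*Protocol*

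**What the plan says.** Section 7.2.10 of the protocol describes Visit 6. Its opening sentence covers patients who reach Day 28 and then adds those who do not: "if possible, when any patient discontinues prior to this visit, the following assessments will be performed". One list follows for both groups. It contains "Study drug administration" and "AIMS, 3 to 6 hours post-dose", with the same timing for BARS and SAS. Nothing in the section exempts discontinuing patients from any item, and it does not refer to Section 7.2.14.

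The Schedule of Assessments in Section 7.1 has a single Visit 6 column for Day 28 and ET. The row "Study Drug Dosing" is marked in it, and the row carries no footnote.

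Other parts of the protocol give different instructions:

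- Sections 4.1.1.1 and 4.1.1.2 open with the same rule: "Dosing of an individual patient will cease if any of the following criteria are met". The criteria are an SAE or another unacceptable risk in the first, and QTcF above 500 msec or a rise of more than 60 msec over Baseline in the second.
- On pregnancy, Section 9.2.3 says "the study drug will be discontinued immediately, and the patient will complete an ET Visit". Schedule footnote o also ends treatment on confirmed positive tests.
- Section 7.2.14 asks the investigator to "complete the follow-up procedures at an ET Visit as follows" and gives a list without dosing. Section 5.3 gives a parallel list, also without dosing.
- Schedule footnote k says that SAS, BARS and AIMS "are to be conducted 3 to 6 hours after the administration of study treatment with the exception of ET Visit".

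**The concern.** A discontinuing patient falls under two sets of instructions. One, in Section 7.2.10 and the dosing row, lists a dose at the visit. The other, in the ET lists and the stopping and pregnancy rules, either lists none or forbids it. The conflict is sharpest for a patient who discontinues because a stopping criterion or a pregnancy requires dosing to cease. Read literally, the Day 28 list has that patient dosed again at the visit that records the discontinuation.

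There is also a smaller data question. AIMS, BARS and SAS are safety endpoints, and an ET rating can be assigned to a scheduled visit under SAP Section 5.2.4. Whether such a rating is taken at a fixed interval after a dose should not depend on which protocol section the site consulted.

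**Working it through.** No arithmetic on power, alpha or sample size applies. The check compares the lists item by item and counts the marks in the dosing row.

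**1. Procedure lists.** Section 7.2.10 has 16 items: concomitant medication, physical examination, weight/BMI/waist, vital signs, ECG, laboratory samples, study drug, pregnancy test, AEs, PANSS, CGI-S, C-SSRS, AIMS, BARS, SAS and Cogstate. Sections 5.3 and 7.2.14 each have 15. The difference is 16 − 15 = 1, and the extra item is study drug. The other 15 procedures match, apart from details such as how the physical examination and the reminder script are worded and the timing of the three EPS scales.

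**2. Dosing row.** From Baseline to the end of treatment the schedule has nine columns: Day 1, Days 2–7, Day 8, Days 9–14, Day 15, Days 16–20, Day 21, Days 22–27, and Day 28 or ET. The dosing row has nine marks, so the ninth falls in the shared column.

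**3. Side by side, for a patient who discontinues before Day 28.**

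| Place in protocol | Dose at the visit? | Post-dose timing for AIMS, BARS, SAS? |
|---|---|---|
| 7.2.10 | Listed, no exception | Yes, no exception |
| Schedule, Day 28/ET column | Marked, no exception | No: footnote k exempts ET |
| 5.3 | Not listed | None given |
| 7.2.14 | Not listed | None given |
| 4.1.1.1, 4.1.1.2 (if a criterion is met) | Dosing ceases | Not addressed |
| 9.2.3 and footnote o (pregnancy) | Treatment is discontinued | Not addressed |

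**4. What follows.**

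- *Dosing.* Section 7.2.10 and the schedule row stand together. They conflict with Sections 5.3 and 7.2.14 for every discontinuing patient who attends an ET visit. They conflict directly with Sections 4.1.1.1, 4.1.1.2 and 9.2.3 and with footnote o only for patients whose dosing must stop under those rules.
- *EPS timing.* Section 7.2.10 stands alone, against footnote k and both ET lists. Its timing also presupposes a dose that day, so the two defects in that section are linked.
- *Source of the conflict.* The one in Section 7.2.10 is in running text and a bulleted list, so it does not depend on how the schedule table was extracted.

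**The case against.** The strongest reply is that no careful site would dose such a patient. The stopping and pregnancy rules are explicit and more specific than a visit list, and footnote o puts the pregnancy rule on the schedule itself. Two sections are dedicated to early termination, and neither contains dosing. Section 5.3 speaks of evaluations at premature discontinuation of dosing. Section 7.2.10 softens its own instruction, calls the items assessments and names Day 28 as the last dosing day. The mark in the shared column is needed because Day 28 is a dosing day.

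Much of this stands. It makes a further dose possible rather than certain, but it does not remove the contradiction. The softening phrase concerns whether the visit procedures can be done, not which of them apply, and the list expressly names drug administration. Footnote k shows that an ET exception was written for the EPS rows; none was written for the dosing row.

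A reader might also infer more than the documents support:

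- *That the schedule imposes post-dose EPS ratings at ET.* It does not; footnote k exempts that visit.
- *That one randomized patient in four is affected, because 25% drop-out is assumed.* That figure is a sample-size assumption, not a rate of ET visits. Section 5.3 recognizes patients lost to follow-up and patients who refuse all end-of-study procedures. The share who meet a safety stopping rule is not stated.
- *That exposure and the treatment-emergent window would be distorted.* A dose actually given belongs in exposure (SAP Section 5.2.7) and rightly moves the window of last dose plus 14 days (SAP Section 5.13.1).
- *That the EPS results would be spoiled.* These scales are summarized descriptively. Varying intervals since the last dose at ET already follow from footnote k and from the untimed ET lists.

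**Conclusion.** The contradiction is real and should be removed. Section 7.2.10 and the dosing row list study drug for patients who discontinue before Day 28. The stopping rules, the pregnancy rules and the two ET lists do not permit or do not include it. Section 7.2.10 also drops the ET exception to EPS timing that footnote k provides.

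This is a stated instruction that goes wrong if followed, not a missing detail. The consequence is that a site could, on a literal reading, give a further dose to a patient stopped for a safety reason. Its frequency cannot be derived from the documents: it depends on how many patients attend an ET visit, why they stopped, and which section the site follows. Sample size, power and type I error are unaffected. The conclusion rests only on the wording of the lists and on the ninth mark of the dosing row lying in the shared column. If that mark were set aside, the conflict in Section 7.2.10 would remain.

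**What to change.** Reconcile Section 7.2.10 and the Day 28/ET column of the schedule in Section 7.1 with Sections 4.1.1.1, 4.1.1.2, 5.3, 7.2.14 and 9.2.3 and with footnotes k and o. One way is to split the shared column into a Day 28 column and an ET column, and to name one governing ET list to which every other section refers. That list should state whether study drug is given at an ET visit, in terms consistent with the stopping and pregnancy rules, and how AIMS, BARS and SAS are timed there. The sponsor decides the clinical rule; the documents need to state it once and consistently.

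The cost is protocol wording and one extra schedule column. No new procedure, patient or analysis is needed.
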